Q2RESEARCH PROTOCOL TEMPLATE INVESTIGATOR INITIATED TREATMENT TRIALS

Title of Project: Treatment of Post-Operative Sinonasal Polyposis with Topical

Furosemide

Principal Investigator: [name], Otolaryngology

Co-Investigators: [name] MD, Otolaryngology; [name],

Otolaryngology; [name], Otolaryngology; [name] PharmD

Abstract

Prior studies have suggested that topical furosemide may reduce the recurrence of sinonasal polyposis following sinus surgery. This project aims to further investigate that claim through a blinded randomized controlled clinical trial following patients who undergo functional sinus surgery for chronic rhinosinusitis with sinonasal polyposis (CRSwP) by randomly assigning participants to receive topical furosemide versus placebo nasal irrigation for 6 weeks post operatively. Outcomes would be compared at 6 months through endoscopic grading scores using Lund Kennedy and Meltzer scores as well as Sino-Nasal Outcome Test (SNOT-22) scores to measure the rate and degree of recurrence and impact on symptoms in the treatment group versus placebo.

A. Specific Aims

State the hypothesis and specific aims. List the long-term objectives and what the proposed research will accomplish.

Hypothesis: Topical furosemide prevents the recurrence of sinonasal polyposis following endoscopic sinus surgery in CRSwP patients

Through investigating this hypothesis, the group aims to provide evidence for treating CRSwP patients with a safe and effective medical therapy to prevent or reduce the recurrence of sinonasal polyposis after sinus surgery. If proven effective in the immediate post operative period, the research would lead to further research aimed at the long term effects of therapy in CRSwP patients to develop a protocol to prevent the recurrence of sinonasal polyps and potentially change the post-operative management of CRSwP patients.

B. Background and Significance

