Performing nasal atomization with 150 mcg twice daily would results in a total exposure of 300 mcg of furosemide daily. Following intranasal administration, a drug may enter systemic circulation through direct local absorption in the nasal mucosa or oral absorption of the swallowed medication¹². When administering intravenous furosemide it has a threshold dose. No diuretic effect is evident at any dose lower than the threshold dose. The threshold dose for intravenous furosemide is 10 mg in a population with normal renal function¹³. Extrapolating this data, a 300 mcg exposure of furosemide should not result in diuresis. A portion of the drug may also be cleared from the sinuses into the throat and swallowed, making it available for gastrointestinal absorption. Furosemide oral solution has a bioavailability of 60%, of that from an intravenous injection of furosemide¹⁴. Therefore swallowed medication should not result in therapeutic levels of furosemide.

After obtaining consent, selected patients will be randomized into 2 groups using the balance block randomization method to either treatment group or placebo group and be scheduled for surgery. Balance block randomization involves the preparation of 4 sheets of paper, writing on 2 sheets "F" for "furosemide" and on 2 sheets "P" for "placebo". The paper sheets will be pooled, placed in a container, and randomly drawn 1 at a time without replacement until all sheets were drawn. The paper sheets will then be placed back into the container and the selection process will be repeated until the sample size is reached. The study investigators will be blinded to the selection process and the randomization will be carried out by the clinical research nurse. A total of 100 patients will be enrolled in the study.

Pre-operatively all patients will receive a 5 day course of 40 mg prednisone, at least one week of and intranasal steroid, and saline irrigation. During a preoperative clinical visit, the degree of sinonasal polyposis will be graded through the Lund Kennedy and Meltzer endoscopic scoring system as well as degree of symptoms through SNOT-22 scores. Also, a demonstration and instructional sheet for how to administer the nasal spray will be distributed at this time.

Then, patients will undergo functional endoscopic surgery as scheduled.

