Immediately post-operatively, patients will begin a 6 week course of twice a day nasal spray If assigned to the treatment group they will receive 300 micrograms of furosemide daily. If assigned to the placebo group, they will receive saline. The clinical research nurse will distribute an unmarked bottle of nasal spray to the study patients either in a pre-operative clinical visit or in the recovery room on the day of surgery. Creation of the study drug will be done by AdvancedRx of Plymouth Meeting, Pa. The department research nurse will store and distribute the study drug to the subjects. Post-operatively, patients will also receive a 40mg prednisone taper (40mg for 3 day, 30mg for 3 days, 20 mg for 3 days, 10 mg for 3 days), nasal saline and a 5-day course of omnicef and at least a 6 week course of intranasal corticosteroid spray. Patients will be given a diary to record any doses that were missed.

Patients taking aminoglycosides will be excluded from this trial as furosemide may increase the ototoxic potential of aminoglycosides. Study subjects who require aminoglycoside use during the study treatment period will be instructed to discontinue taking the study drug and will be removed from the study.

Post-operative visits will be scheduled at 1 week, 3 week, 2 month, 4 month and 6 month intervals. The post-operative visits may be scheduled within 4 days of the scheduled interval. Post-operatively, the degree of nasal polyposis will again be graded through the Lund Kennedy and Meltzer endoscopic scoring system as well as degree of symptoms through SNOT-22 scores. These scores will be obtained at the 2, 4 and 6 month visit.

The duration of participation for the study will be 6 months. Early termination criteria are serious adverse reactions, inability to recruit or adequately enroll an adequate number of patients, problems arise in the study medicine's stability or manufacturing and new toxicological findings that affect the benefit-to-risk ratio.

E. Statistical Methods

If not a pilot study, provide biostatistical design, power calculations determining the number of participants , and the proposed analysis. (suggested length: $\frac{1}{2}$ page)

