Based on prior randomized controlled clinical trials, the study is powered to achieve at least 80% power. Based on the results published by Hashemian et al.¹, Group sample sizes of 40 in ctrl and 40 in treat achieve 95% power to detect a difference of 38% vs. 79% using two-sided Fisher's Exact Test with significance level 5%. Also based on results published by Passali et al.², group sample sizes of 47 in ctrl and 47 in treat achieve 80% power to detect a difference of 30% vs. 6% using two-sided Fisher's Exact Test with significance level 5%.

The primary outcomes will be compared through the independent t test for continuous variables and the Fischer exact test for nominal variables. All statistical analyses will be performed at a significance level of 0.05.

F. Gender/Minority/Pediatric Inclusion for Research

All protocols must include documentation of the inclusion of women and minorities in the research protocol. If women and minorities are not to be included, provide rationale for exclusion.

The study will include women and minorities.

G. Human Subjects

1. Provide number, age range, and health status of the subject population. List criteria for inclusion or exclusion.

100 patients, 18 to 65 years old, chronic rhinosinusitis with sinonasasl polyposis

Inclusion Criteria:

Patients with chronic rhinosinusitis and sinonasal polyposis who are candidates for functional endoscopic sinus surgery

Exclusion Criteria:

Hypersensitivity to furosemide or sulfonamides, pregnancy, history of tinnitus, history of sensorineural hearing loss, poorly controlled diabetes, current diuretic therapy, known electrolyte disorder, currently taking aminoglycosides, BUN and creatinine levels out of the normal range, history of renal disease, allergy to sulfonamides.

2. Identify sources of research material in the form of specimens, records or data.

Patient medical record, physical exam findings (endoscopic scores), SNOT-22 questionnaire,

3. Describe plans for recruitment and consent procedures to be followed.

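### Lund Kennedy, Meltzer and SNOT-22 are all scored before surgery, but Section E plans only an unadjusted t test; ANCOVA on the pre-operative score costs almost nothing and may add precision.

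*Combined protocol and SAP*

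**What the plan says.** Section E (Statistical Methods) gives one rule for continuous outcomes: they will be "compared through the independent t test for continuous variables". Nominal outcomes get Fisher's exact test. The section mentions no covariate, change score or model.

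The Abstract names the outcomes and the time point: "Outcomes would be compared at 6 months through endoscopic grading scores using Lund Kennedy and Meltzer scores", together with SNOT-22.

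Section D (Research Design and Methods) provides for a grading at a pre-operative visit: "sinonasal polyposis will be graded through the Lund Kennedy and Meltzer endoscopic scoring system as well as degree of symptoms through SNOT-22 scores". Study spray starts only after the operation. On the follow-up scores, Section D says: "These scores will be obtained at the 2, 4 and 6 month visit".

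The sample size in Section E rests on binary recurrence rates alone. The smaller of its two effects is the one for which 47 per arm "achieve 80% power to detect a difference of 30% vs. 6% using two-sided Fisher's Exact Test". No SD, target difference or power is given for any of the three scores.

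**The concern.** The pre-operative value of each score is measured before study treatment can affect it, so it is a legitimate covariate. It is collected in any case, and the stated analysis does not use it. If it predicts the 6-month value, adjusting for it removes part of the between-patient variation and narrows the interval for the treatment difference. It also corrects for chance imbalance in baseline severity, which the blocks of four, with no stratification described, do not control.

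Neither bias nor type I error is at issue. What is at stake is the precision of three comparisons for which the plan states no power.

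**Working it through.** **The plan's own figures.** These concern binary recurrence only. The continuity-corrected two-proportion formula gives 40 per arm for 38% vs 79% at 95% power and 47 per arm for 30% vs 6% at 80% power, both as stated. Exact Fisher power at those sizes is 95.6% and 82.5%. The sizing therefore reproduces, and changing the analysis of the scores does not touch it.

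**Inputs from the documents.** Section D: "A total of 100 patients will be enrolled in the study", in blocks of four with two per arm, hence n = 50 per arm. Section E: 5% significance level.

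**Assumed.** A two-sided t test (Section E states sidedness only for Fisher's test), every patient scored at both times, normally distributed scores, and a true difference of 0.5 SD. Rho is shown as a range.

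**Formulas.** Power is from the noncentral t distribution, with variance of the difference = (2/50) × factor, in SD² units.

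- t test on the 6-month score: factor 1, df = 100 − 2 = 98.
- ANCOVA with one covariate: factor = (1 − rho²) × (1 + 1/(100 − 4)) = (1 − rho²) × 97/96, df = 97. The 97/96 is the cost of estimating the slope.
- 95% CI half-width = t(0.975, df) × √(0.04 × factor). For the t test this is 1.984 × 0.2 = 0.397 SD.
- Equivalent change in sample size = 1/factor − 1. At rho 0.3 the factor is 0.91 × 97/96 = 0.9195, and 1/0.9195 − 1 = +9%.

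**Results at 0.5 SD.** The t test has 69.7% power and a half-width of 0.397 SD.

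| rho | ANCOVA power | Change (points) | Half-width (SD) | Equivalent sample size |
|---|---|---|---|---|
| 0 | 69.2% | −0.5 | 0.399 | −1% |
| 0.1 | 69.7% | 0.0 | 0.397 | 0% |
| 0.2 | 71.0% | +1.3 | 0.391 | +3% |
| 0.3 | 73.3% | +3.6 | 0.381 | +9% |
| 0.4 | 76.6% | +6.9 | 0.366 | +18% |
| 0.5 | 81.1% | +11.5 | 0.346 | +32% |
| 0.6 | 86.8% | +17.1 | 0.319 | +55% |

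Changes are taken before rounding.

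**Break-even.** Setting the factor to 1 gives rho = √(1 − 96/97) = 0.10.

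**Other effect sizes.**

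| Difference | t test | ANCOVA, rho 0 | rho 0.2 | rho 0.3 | rho 0.5 |
|---|---|---|---|---|---|
| 0.3 SD | 31.8% | 31.5% | 32.6% | 34.1% | 40.0% |
| 0.8 SD | 97.7% | 97.6% | 98.0% | 98.5% | 99.5% |

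Across effects from 0.1 to 1.2 SD, the largest loss at rho 0 was 0.46 points.

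**Incomplete follow-up.** With 40 scored per arm and 0.5 SD, the t test has 59.8%, and ANCOVA has 59.2%, 63.3% and 71.7% at rho 0, 0.3 and 0.5. The pattern is the same.

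**Simulation.** With 200,000 trials per rho at 50 per arm and 0.5 SD, ANCOVA power was 69.3, 70.0, 71.1, 73.3, 76.6, 81.2 and 86.8% for rho 0 to 0.6. Type I error was 4.9 to 5.0% for both methods.

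**The case against.** The strongest objection is that nothing here is wrong: a valid test is pre-specified, and preferring ANCOVA is a matter of efficiency. That stands, and it is why this is an optional improvement.

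Second, the benefit cannot be established from the documents. Rho is not given and may be low. Between the two measurements, Section D has this: "Then, patients will undergo functional endoscopic surgery as scheduled". It adds: "Post-operatively, patients will also receive a 40mg prednisone taper". If post-operative endoscopic scores also cluster at zero, the gain shrinks. In an illustrative check with 50–70% of 6-month scores at zero (an assumption), an underlying correlation of 0.3 became 0.23–0.26, and the gain at 0.5 SD fell from 3.6 to about 2–2.5 points. At 0.8 SD the gain is under 2 points even at rho 0.5. All this stands too. The case rests on the asymmetry between a very small maximum loss and a possibly useful gain.

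Third, Section E does not list its continuous variables, nor say whether the t test is on the 6-month value or on change from baseline. That the three scores get it is an inference, though they are the only numeric outcomes named. The change-score reading would use the baseline but does not rescue the plan. Its variance factor is 1 + k² − 2k·rho, where k is the pre-operative SD divided by the 6-month SD, so it beats the raw score only when rho exceeds k/2. At rho 0.3 and 0.5 SD its power is 71.9, 55.3 and 36.5% for k = 0.5, 1 and 1.5, against 73.3% for ANCOVA.

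Finally, Section D does not say whether the pre-operative grading comes before or after the pre-operative prednisone course, and a patient without a pre-operative score would drop out of a simple ANCOVA. Both are drafting points for the fix.

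**Conclusion.** The point holds as an optional improvement. Section E names no adjustment for a baseline that the trial already collects on all three scores. The unadjusted t test is valid; the only loss is precision, and only if rho exceeds about 0.10. At 50 per arm, ANCOVA costs at most about 0.5 points of power. At an assumed 0.5 SD difference it gains about 4 points at rho 0.3 and 11 at rho 0.5, equivalent to 9% and 32% more patients. These gains depend on an assumed effect size, on scores that are close to normal and on an unknown rho; the gain may be about nil. Neither the planned 100 patients nor the stated power for recurrence is affected.

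**What to change.** In Section E, replace the t test for these scores with wording such as: *For Lund Kennedy, Meltzer and SNOT-22, the 6-month score will be compared between arms by ANCOVA with arm and the pre-operative value of the same score as terms; the adjusted mean difference will be reported with its 95% CI.* Leave Fisher's exact test for nominal outcomes unchanged.

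Also state which pre-operative assessment is the baseline, including its timing relative to the pre-operative prednisone course, and how a missing pre-operative score will be handled so that the patient stays in the analysis. Make the change before unblinding, so that there is no later choice between adjusted and unadjusted results.

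The cost is a sentence or two of text and one degree of freedom. No new data, patients or visits are needed.

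### Optional gain: replacing the planned, valid Fisher test with Boschloo's exact test would raise power for 30% vs 6% from 85.7% to 89.1% at 50 evaluable patients per arm

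*Combined protocol and SAP*

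**What the plan says.** Section E (Statistical Methods) assigns the t test to continuous outcomes and "the Fischer exact test for nominal variables". It adds: "All statistical analyses will be performed at a significance level of 0.05".

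The power statements in the same section use the two-sided Fisher test at 5%. The target is that "the study is powered to achieve at least 80% power". Two scenarios from earlier trials support it:

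- "Group sample sizes of 40 in ctrl and 40 in treat achieve 95% power to detect a difference of 38% vs. 79"%.
- "group sample sizes of 47 in ctrl and 47 in treat achieve 80% power to detect a difference of 30% vs. 6"%.

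The second scenario needs more patients and so sets the sample size. Section D (Research Design and Methods) states: "A total of 100 patients will be enrolled in the study". Allocation is 1:1 in blocks of four, which gives 50 per arm. No drop-out rate is stated. Neither section discusses the conservatism of Fisher's test or an unconditional exact alternative.

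**The concern.** Fisher's test conditions on the total number of events. With samples this small, the attainable p-values are few, so the test usually runs well below its nominal level. The plan accepts a 5% false-positive risk but does not receive the power that goes with it.

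Power matters here because enrolment exceeds the 94 patients (2 × 47) of the larger scenario by only 6. Some loss is foreseeable: follow-up lasts six months, and Section D removes participants who need an aminoglycoside during treatment. A test that recovers unused error without extra patients would widen that margin.

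**Working it through.** **Inputs.** From Section E: two-sided α = 0.05, and rates of 30% vs 6% and 38% vs 79%. From Section D: 100 patients, 1:1, so 50 per arm. Assumption: all 50 are evaluable unless a smaller number is given.

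**Step 1: reproduce the plan's sample sizes.** Use the pooled-variance formula with continuity correction, where p̄ is the mean of the two rates and d their difference:

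n₀ = [1.960·√(2p̄(1−p̄)) + z_power·√(p₁(1−p₁)+p₂(1−p₂))]² / d²

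n = (n₀/4)·[1+√(1+4/(n₀d))]²

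- 30% vs 6%, 80% power: p̄ = 0.18, d = 0.24. n₀ = (1.960 × 0.5433 + 0.842 × 0.5161)² / 0.0576 = 39.03, and n = 46.99, rounded up to **47**, as stated.
- 38% vs 79%, 95% power: p̄ = 0.585, d = 0.41. n₀ = 34.49, and n = 39.22, rounded up to **40**, as stated.

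Exact power of the two-sided Fisher test, summed over all two-binomial tables, is 82.5% at 47 per arm and 95.6% at 40 per arm. Both stated powers are met.

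**Step 2: true size of Fisher's test at 50 per arm.** Size at common rate p is the sum of Bin(x; 50, p)·Bin(y; 50, p) over all tables with Fisher p ≤ 0.05.

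| Common rate | Fisher | Boschloo |
|---|---|---|
| 6% | 1.0% | 2.6% |
| 18% (midpoint of 30% and 6%) | 2.7% | 3.9% |
| 30% | 3.1% | 4.2% |
| 58.5% (midpoint of 38% and 79%) | 3.3% | 4.8% |
| Maximum over all rates | 3.5% | 4.9% |

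**Step 3: Boschloo's test.** It orders tables by the Fisher p-value. It then takes the largest cut-off whose size, maximised over a fine grid of common rates, stays at or below 5%. At 50 per arm the cut-off is 0.0693 and the maximum size 4.87%. Because the cut-off exceeds 0.05, the rejection region contains Fisher's, so power cannot be lower at any pair of rates.

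**Step 4: power for 30% vs 6%.**

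| Evaluable per arm | Fisher | Boschloo | Gain (points) |
|---|---|---|---|
| 50 | 85.7% | 89.1% | 3.4 |
| 47 | 82.5% | 88.3% | 5.8 |
| 44 | 80.0% | 85.5% | 5.5 |
| 43 | 78.9% | 84.4% | 5.5 |
| 40 | 76.8% | 80.9% | 4.1 |
| 39 | 75.3% | 79.6% | 4.3 |

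Fisher's power is below 80% at every size under 44. Boschloo's is at least 80% from 40 to 50. The tolerable loss from 50 per arm therefore rises from 6/50 = 12% to 10/50 = 20%.

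**Step 5: the other scenario.** For 38% vs 79% at 50 per arm, power moves from 98.6% to 99.1%.

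**Step 6: an example table.** With 12/50 vs 4/50, Fisher p = 0.054 and Boschloo p = 0.035, with the arm sizes as the fixed margin. Entering the same table transposed, so that the event totals (16 and 84) are held fixed, gives 0.030, which answers a different question.

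**The case against.** The strongest reply is that nothing here is wrong. Power calculation and analysis both use Fisher's test, the sample sizes reproduce, and enrolment exceeds the number required. All of that stands. A reader might infer from the low size that the plan is invalid or misses its power target; the documents do not support either reading.

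A reader might also take the roughly halved error rate as holding for all the planned rates. It describes 30% vs 6% only. For 38% vs 79% the size is about two-thirds of nominal and the power gain is half a point. Nor is the 5.8-point gain at 47 per arm typical. It is partly an effect of discreteness: Boschloo's power drops to 87.4% at 48 per arm before rising again.

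A third reply is that Fisher's test can be justified by random assignment alone, whereas Boschloo's guarantee needs two independent binomials. That is a fair limit. But the plan's own power calculation already compares two proportions on that footing, so the switch adds no new assumption to the design.

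The attrition argument should not be pushed further than it goes. No drop-out rate is given, so nobody can say from the documents that evaluable numbers will fall to 40 to 43 per arm, the only range where the choice of test decides whether 80% is reached.

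Finally, Section E gives no score cut-off that turns the endoscopic grades into recurrence yes or no. That definition comes first; the choice of test applies once it is fixed.

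**Conclusion.** The point holds as an efficiency gain of low severity. Fisher's test is valid and adequate for the stated target. Boschloo's test would add about 3 to 6 points of power for 30% vs 6% across 40 to 50 evaluable per arm, with the type I error still capped at 5% and no extra patients. For 38% vs 79% at full enrolment the gain is negligible.

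The figures assume equal evaluable arms, independent binomial outcomes, a binary recurrence endpoint, and true rates equal to those the plan borrows from earlier trials. The sponsor cannot know which scenario will apply; the gain falls in the one with the smaller margin.

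**What to change.** In Section E, before unblinding:

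1. Name Boschloo's two-sided unconditional exact test at 5% for the recurrence comparison. State that tables are ordered by the two-sided Fisher p-value and that the arm sizes are the fixed margin.
2. Report the risk difference with an exact unconditional 95% confidence interval.
3. State power as 89% for 30% vs 6% if all 50 per arm are evaluable, alongside the 38% vs 79% result (99.1%).

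The cost is a few sentences, and the test is available in standard software. There are three small downsides. Clinical readers know the test less well. Its p-value depends on which margin is treated as fixed, so the table orientation must be checked in the program. Its error guarantee rests on the two-binomial model. If the sponsor prefers to keep Fisher's test, the plan remains valid as written.
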